### 10.3.4 Handling of patients after permanent treatment discontinuation

Patients will be followed-up according to the study procedures as specified in this protocol up to the scheduled date of study completion, or up to recovery or stabilization of any AE to be followed-up as specified in this protocol, whichever comes last.

If possible, and after the permanent discontinuation of treatment, the patients will be assessed using the procedure normally planned for the last dosing day with the IMP (EOT Visit). (Refer to [Section 10.1.14](#) Visit 10 (Week 52): End of treatment).

Patients who discontinue early from treatment may be asked to return to the clinic to have additional ADA samples collected for analysis based on the overall clinical presentation at the time of discontinuation.

Patients who permanently discontinue the study medication will be asked and encouraged to return to the clinic for and participate in follow-up assessments described in ([Section 10.3.1](#)).

### **10.3.5 Procedure and consequence for patient withdrawal from study**

The patients may withdraw from the study before study completion if they decide to do so, at any time and irrespective of the reason. Withdrawal of consent for treatment should be distinguished from withdrawal of consent for follow-up visits and from withdrawal of consent for non-patient contact follow-up, eg, medical records check. Patients requesting withdrawal should be informed that withdrawal of consent for follow-up may jeopardize the public health value of the study. If possible, the patients should be assessed using the procedures normally planned at the end-of-treatment visit.

Patients who withdraw should be explicitly asked about the contribution of possible AEs to their decision to withdraw consent, and any AE information elicited should be documented. Preferably the patient should withdraw consent in writing and, if the patient or the patient's representative refuses or is physically unavailable, the site should document and sign the reason for the patient's failure to withdraw consent in writing.

All study withdrawals should be recorded by the Investigator in the appropriate screens of the e-CRF and in the patient's medical records when considered as confirmed. In the medical record, at least the date of the withdrawal and the reason should be documented.

For patients who fail to return to the site, unless the patient withdraws consent for follow-up, the Investigator should make the best effort to recontact the patient (eg, contact patient's family or private physician, review available registries or health care databases), and to determine his/her health status, including at least his/her vital status. Attempts to contact such patients must be documented in the patient's records (eg, times and dates of attempted telephone contact, receipt for sending a registered letter). A patient should only be designated as lost to follow-up if the site is unable to establish contact with the patient after 3 documented attempts via 2 different methods (phone, text, e-mail, certified letter, etc).

The statistical analysis plan (SAP) will specify how these patients lost to follow-up for their primary endpoints will be considered.

Patients who have withdrawn from the study cannot be re-randomized (treated) in the study. Their inclusion and treatment numbers must not be reused.

## **10.4 OBLIGATION OF THE INVESTIGATOR REGARDING SAFETY REPORTING**

### **10.4.1 Definitions of adverse events**

#### **10.4.1.1 Adverse event**

An AE is any untoward medical occurrence in a patient or clinical investigation patient administered a pharmaceutical product and which does not necessarily have to have a causal relationship with this treatment.

#### **10.4.1.2 Serious adverse event**

An SAE is any untoward medical occurrence that at any dose:

- Results in death, or.
- Is life-threatening, or.
- Note: The term “life-threatening” in the definition of “serious” refers to an event in which the patient was at risk of death at the time of the event; it does not refer to an event which hypothetically might have caused death if it were more severe.
- Requires inpatient hospitalization or prolongation of existing hospitalization, or.
- Results in persistent or significant disability/incapacity, or.
- Is a congenital anomaly/birth defect.
- Is a medically important event.

Medical and scientific judgment should be exercised in deciding whether expedited reporting is appropriate in other situations, such as important medical events that may not be immediately life-threatening or result in death or hospitalization but may jeopardize the patient or may require medical or surgical intervention (ie, specific measures or corrective treatment) to prevent one of the other outcomes listed in the definition above.

Note: The following list of medically important events is intended to serve as a guideline for determining which condition has to be considered as a medically important event. The list is not intended to be exhaustive:

- Intensive treatment in an emergency room or at home for:
  - Allergic bronchospasm,
  - Anaphylaxis (refer to [Appendix H](#) for Definition of Anaphylaxis),
  - Blood dyscrasias (ie, agranulocytosis, aplastic anemia, bone marrow aplasia, myelodysplasia, pancytopenia, etc),
  - Convulsions (seizures, epilepsy, epileptic fit, absence, etc).
- Development of drug dependence or drug abuse.
- ALT >3 x ULN + total bilirubin >2 x ULN.
- Suicide attempt or any event suggestive of suicidality.
- Syncope, loss of consciousness (except if documented as a consequence of blood sampling).
- Bullous cutaneous eruptions.
- Cancers diagnosed during the study or aggravated during the study.
- Chronic neurodegenerative diseases (newly diagnosed) or aggravated during the study.

### 10.4.1.3 Adverse event of special interest

An adverse event of special interest (AESI) is an AE (serious or non-serious) of scientific and medical concern specific to the Sponsor's product or program, for which ongoing monitoring and immediate notification by the Investigator to the Sponsor is required. Such events may require further investigation in order to characterize and understand them. Adverse events of special interest may be added or removed during a study by protocol amendment.

For these AESIs, the Sponsor will be informed immediately (ie, within 24 hours), per SAE notification described [Section 10.4.4](#), even if not fulfilling a seriousness criterion.

AESIs for this study include:

- Anaphylactic or systemic allergic reactions that are related to IMP and that require treatment (refer to [Appendix H](#) for the definition of anaphylaxis).
- Severe injection site reactions that last longer than 24 hours.
- Any infection meeting at least 1 of the following criteria:
  - Any serious infection (SAE),
  - Requires parenteral (IV, IM, SC) antimicrobial therapy,
  - Requires oral antimicrobial therapy for longer than 2 weeks,
  - Is a parasitic infection,
  - Is an opportunistic infection (refer to [Appendix I](#)).

**Note:** Antimicrobial therapy refers to antibiotic, antiviral, and antifungal agents.

- Significant elevation of ALT.
  - ALT  $>5 \times$  ULN in patients with baseline ALT  $\leq 2 \times$  ULN;
  - or
  - ALT  $>8 \times$  ULN if baseline ALT  $>2 \times$  ULN
- Pregnancy occurring in a female patient entered in the clinical trial or in a female partner of a male patient entered in the clinical trial. It will be qualified as an SAE only if it fulfills 1 of the seriousness criteria (see [Section 10.4.1.2](#)).
  - In the event of pregnancy in a female participant, IMP should be discontinued.
  - Follow-up of the pregnancy in a female participant or in a female partner of a male participant is mandatory until the outcome has been determined.
- Symptomatic overdose (serious or non-serious) with IMP/NIMP
  - An overdose (accidental or intentional) with the IMP/NIMP is an event suspected by the Investigator or spontaneously notified by the patient (not based on systematic syringes or pills count) and defined as at least twice the intended dose during an interval of less than 11 days. The circumstances (ie, accidental or intentional) should be clearly specified in the verbatim and symptoms, if any, entered on separate AE forms.

Of note, asymptomatic overdose has to be reported as a standard AE.

#### **10.4.2 Serious adverse events waived from expedited regulatory reporting to regulatory authorities**

Not applicable for this study.

#### **10.4.3 General guidelines for reporting adverse events**

All AEs, regardless of seriousness or relationship to IMP/NIMP, spanning from the signature of the informed consent form until the end of the study as defined by the protocol for that patient, are to be recorded on the corresponding page(s) or screen(s) of the e-CRF.

Whenever possible, diagnosis or single syndrome should be reported instead of symptoms. The Investigator should specify the date of onset, intensity, action taken with respect to IMP, corrective treatment/therapy given, additional investigations performed, outcome, and his/her opinion as to whether there is a reasonable possibility that the AE was caused by the IMP or by the study procedure(s).

The Investigator should take appropriate measures to follow all AEs until clinical recovery is complete and laboratory results have returned to normal, or until progression has been stabilized, or until death, in order to ensure the safety of the patients. This may imply that observations will continue beyond the last planned visit per protocol, and that additional investigations may be requested by the monitoring team up to as noticed by the Sponsor.

When treatment is prematurely discontinued, the patient's observations will continue until the end of the study as defined in [Section 10.3.1](#).

Laboratory, vital signs or ECG abnormalities are to be recorded as AEs only if:

- Symptomatic and/or,
- Requiring either corrective treatment or consultation, and/or,
- Leading to IMP discontinuation or modification of dosing, and/or,
- Fulfilling a seriousness criterion, and/or,
- Defined as an AESI.

See [Section 10.4.6](#) for a table summarizing reporting timelines.

#### **10.4.4 Instructions for reporting serious adverse events**

In the case of occurrence of an SAE, the Investigator or any designee must immediately:

- ENTER (within 24 hours) the information related to the SAE in the appropriate screens of the e-CRF; the system will automatically send a notification to the monitoring team after approval of the Investigator within the e-CRF or after a standard delay.
- SEND (preferably by fax or e-mail) a photocopy of all examinations carried out and the dates on which these examinations were performed, to the representative of the monitoring team whose name, fax number, and email address appear on the clinical trial protocol. Care should be taken to ensure that the patient's identity is protected and the patient's identifiers

in the clinical trial are properly mentioned on any copy of a source document provided to the Sponsor. For laboratory results, include the laboratory normal ranges.

- All further data updates should be recorded in the e-CRF as appropriate, and further documentation as well as additional information (for laboratory data, concomitant medications, patient status, etc) should be sent (by fax or e-mail) to the monitoring team within 24 hours of knowledge. In addition, every effort should be made to further document any SAE that is fatal or life threatening within a week (7 days) of the initial notification.
- A back-up plan (using a paper CRF process) is available and should be used when the e-CRF system does not work.

Any SAE brought to the attention of the Investigator at any time after the end of the study for the patient and considered by him/her to be caused by the IMP with a reasonable possibility, should be reported to the monitoring team.

#### **10.4.5 Guidelines for reporting adverse events of special interest**

For AESIs, the Sponsor must be informed immediately (ie, within 24 hours), as per SAE notification guidelines described in [Section 10.4.4](#), even if not fulfilling a seriousness criterion, using the corresponding pages of the CRF (to be sent) or screens in the e-CRF.

Instructions for AE reporting are summarized in [Table 4](#).

#### **10.4.6 Guidelines for management of specific laboratory abnormalities**

Decision trees for the management of certain laboratory abnormalities by Sanofi are provided in [Appendix G](#).

The following laboratory abnormalities should be monitored, documented, and managed according to the related flow chart in protocol appendices.

- Neutropenia.
- Thrombocytopenia.
- Increase in ALT.
- Acute renal insufficiency.
- Suspicion of rhabdomyolysis.

In addition, on treatment eosinophil counts >3000 cells/ $\mu$ L (3.0 G/L) are to be reported as AEs.

NOTE: In this clinical trial these laboratory abnormalities can be considered as AESIs (see [Section 10.4.1.3](#)).

**Table 4 - Summary of adverse event reporting instructions**

Adverse event/laboratory abnormality		Reporting timeframe
Serious adverse event		Within 24 hours
Adverse Event (non-SAE, non-AES) a		Routine
Pregnancy b		Within 24 hours
Overdose	Symptomatic	Within 24 hours
	Asymptomatic	Routine
ALT elevation	ALT >5 ULN if baseline ALT is ≤2 ULN	Within 24 hours
	ALT >8 ULN if baseline ALT is >2 ULN	Within 24 hours
Anaphylactic or systemic allergic reactions that are related to IMP and that require treatment		Within 24 hours
Severe injection site reactions that last longer than 24 hours		Within 24 hours
Infections as defined in Section 10.4.1.3		

ALT=alanine aminotransaminase; ULN=upper limit of normal.

*a* For reporting of epistaxis as an AE, use both AE form and Safety complementary form to provide date, features and outcome of the event.

*b* The drug exposure via parent form is not part of the Case Report Form, but needs to be completed for pregnancy

## 10.5 OBLIGATIONS OF THE SPONSOR

During the course of the study, the Sponsor will report in an expedited manner:

- All SAEs that are both unexpected and at least reasonably related to the IMP (SUSAR), to the regulatory authorities, Institutional Review Board/Independent Ethics Committee as appropriate and to the Investigators.
- All SAEs that are expected and at least reasonably related to the IMPs to the regulatory authorities, according to local regulations.

Any other AE not listed as an expected event in the Investigator's Brochure or in this protocol will be considered unexpected.

For safety, the treatment code will be unblinded by the Sponsor for reporting to the Health Authorities.

Authority of any suspected unexpected adverse drug reaction (SUSAR) and reasonably associated with the use of the IMP according to either the judgment of the Investigator and/or the Sponsor.

In case of a SUSAR, Sanofi Global Pharmacovigilance and Epidemiology will utilize XGRID to reveal medication assignment for regulatory reporting requirements for the particular case.

The Sponsor will report all safety observations made during the conduct of the trial in the CSR.

## 10.6 SAFETY INSTRUCTIONS

### 10.6.1 Hypersensitivity

Allergic reaction is a potential risk associated with the administration of most therapeutic mAB treatments.

Allergic reactions may be defined as allergic reaction-mediated signs and symptoms experienced by patients during or shortly after the pharmacologic or biologic agent is given. These reactions may present in a variety of ways, including dizziness, headache, anxiety, dyspnea, hypotension, tachycardia, pruritus, rash, urticaria/angioedema, flushing, nausea, or vomiting, and joint pain with fever. Allergic reactions may begin within a few hours and persist up to 24 hours post dosing. Refer to [Appendix H](#) "Definition of Anaphylaxis", which describes the clinical criteria for the diagnosis of anaphylaxis.

Patients should be monitored for at least 30 minutes (or minimum time required by your local regulator) after each study-site administered IMP administration for any signs or symptoms of a hypersensitivity reaction. Any instance of allergic reaction should be reported as an AESI. Any anaphylactic reactions or acute allergic reactions that require immediate treatment will be an AESI with immediate reporting (within 24 hours) and study medication must be permanently discontinued. Trained personnel and medications should be available to treat anaphylaxis or any severe allergic reaction if it occurs. Furthermore, the study patients will be advised, when the IMP is administered at home, to self-monitor for potential signs and symptoms that may suggest a hypersensitivity reaction for at least 30 minutes after administration.

Anaphylactic reactions or systemic allergic reactions that are related to IMP and require treatment must be reported as an adverse event of special interest (AESI) (within 24 hours, for further details, see AESI definition in [Section 10.4.1.3](#) and [Appendix H](#)) and study medication must be permanently discontinued. ADA and PK samples will be collected near the onset and completion resolution of the AESI for any additional analysis

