### 10.3.3 List of criteria for permanent treatment discontinuation

The patients may withdraw from treatment with the IMP if they decide to do so, at any time and irrespective of the reason, or this may be the Investigator's decision. All efforts should be made to document the reasons for treatment discontinuation and this should be documented in the e-CRF.

Patients must be withdrawn from the study (ie, from any further IMP or study procedure) for the following reasons:

- At their own request or at the request of their legally authorized representative (legally authorized representative means an individual or judicial or other body authorized under applicable law to consent on behalf of a prospective patient to the patient's participation in the procedure(s) involved in the research).
- If, in the Investigator's opinion, continuation in the study would be detrimental to the patient's well-being.

In case of surgery for NP (refer to [Section 9.2.1.5](#) for details).

- At the specific request of the Sponsor.
- In the event of a critical protocol deviation, at the request of the Investigator or the Sponsor.
- Any code broken requested by the Investigator will lead to permanent treatment discontinuation.
- In the event of an anaphylactic systemic allergic reaction that is related to IMP and that requires treatment.
- In the event that the patient is diagnosed with a malignancy during the study, excluding carcinoma in situ of the cervix or squamous or basal cell.
- Pregnancy.
- Any opportunistic infection, such as tuberculosis or other infections whose nature or course may suggest an immunocompromised status (refer to [Appendix I](#)).
- Serum ALT >3 ULN and total bilirubin >2ULN.
- Serum ALT >5 ULN if baseline ALT <2 ULN or ALT >8 ULN if baseline ALT >2 ULN.

Stopping rules described in [Appendix G](#) should be applied.

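### The mandatory stop list in Protocol 10.3.3 is narrower than the permanent-stop rules for allergic reactions in 10.6.1, and the AESI wording for these reactions differs between sections

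*Protocol*

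**What the plan says.** Protocol 10.6.1 (Hypersensitivity) deals with allergic reactions in three sentences:

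- A general reporting rule: "Any instance of allergic reaction should be reported as an AESI".
- A first stop trigger, for anaphylactic or acute reactions: "acute allergic reactions that require immediate treatment will be an AESI with immediate reporting (within 24 hours) and study medication must be permanently discontinued". It sets no condition on relatedness and does not require the reaction to be systemic.
- A second stop trigger: "Anaphylactic reactions or systemic allergic reactions that are related to IMP and require treatment must be reported as an adverse event of special interest", again with permanent discontinuation. Here the treatment need not be immediate, but the reaction must be related to the study drug.

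The list of mandatory reasons for stopping in 10.3.3 has one item on allergy: "In the event of an anaphylactic systemic allergic reaction that is related to IMP and that requires treatment".

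The AESI list in 10.4.1.3 gives "Anaphylactic or systemic allergic reactions that are related to IMP and that require treatment", and Table 4 repeats that item with a 24-hour time limit. Section 10.4.5 applies the same limit to every AESI: "For AESIs, the Sponsor must be informed immediately (ie, within 24 hours". Section 10.4.1.3 also says how the list may change: "Adverse events of special interest may be added or removed during a study by protocol amendment".

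**The concern.** Section 4.5 singles out systemic hypersensitivity as an important potential risk, so the rule for when a patient must never be re-exposed should read the same wherever a site looks it up. It does not. The list headed as the criteria for permanent discontinuation is the shortest version, while the fuller version sits in the safety instructions.

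The surrounding text leans towards keeping patients on drug. Section 10.3 asks sites to consider first whether a stop can be temporary, and 10.3.2 allows an interruption for an adverse event followed by a restart. A site that checks only 10.3.3 after a treated systemic reaction could therefore pause and resume where 10.6.1 requires a permanent stop.

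The AESI wording raises a lesser issue. If sites differ on which allergic reactions to flag, they will differ in what reaches the sponsor within 24 hours, in the AESI data that the data monitoring committee reviews (Protocol 6.4.1), and in the separate summary of investigator-reported AESIs in SAP 2.4.5.1.

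**Working it through.** The plan gives no figure on this point and no arithmetic applies. The check is to put the stop rules side by side and ask which reactions each one covers. The first trigger is read with immediate treatment qualifying both anaphylactic and acute reactions.

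| Illustrative reaction | 10.6.1, first trigger | 10.6.1, second trigger | 10.3.3 as written | 10.3.3 with *or* restored |
|---|---|---|---|---|
| Related anaphylaxis, treated at once | stop | stop | stop | stop |
| Related acute systemic reaction, not anaphylaxis, treated at once | stop | stop | not listed | stop |
| Related systemic reaction, not anaphylaxis, treated later | not covered | stop | not listed | stop |
| Related acute reaction, not systemic, treated at once | stop | not covered | not listed | not listed |
| Acute reaction judged unrelated, treated at once | stop | not covered | not listed | not listed |

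The rows are examples chosen to separate the rules. They are not a count and say nothing about frequency.

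Three results follow.

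1. Neither trigger in 10.6.1 contains the other. The first adds unrelated and non-systemic reactions. The second adds related systemic reactions whose treatment is not immediate.
2. The 10.3.3 item as written is narrower than both triggers. It requires the reaction to be anaphylactic as well as systemic, related and treated.
3. Restoring *or* makes 10.3.3 equal to the second trigger only. Reactions covered by the first trigger alone remain off the list.

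The missing *or* is probably a drafting slip. The word stands in 10.4.1.3, in Table 4, in 9.5.1.1 (the sampling rule) and in 10.6.1 itself.

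For AESI status, the general sentence in 10.6.1 covers every allergic reaction, including mild, untreated or unrelated ones. The item in 10.4.1.3 and Table 4 is limited to anaphylactic or systemic reactions that are related and treated. The last paragraph of 10.6.1 sends the reader to 10.4.1.3 for the AESI definition, so that section points to a narrower rule than one of its own sentences.

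**The case against.** The best defence is that a site following the whole protocol breaches nothing. Section 10.6.1 is the dedicated section and says twice that drug must be stopped for good, so a careful reader would apply both triggers together. Section 10.3.2 is also not an open door: a restart needs close monitoring and the investigator's judgment that the event is sufficiently resolved and unlikely to recur. Section 10.3.3 separately requires withdrawal when the investigator thinks that continuing would harm the patient. All of this stands and limits the harm. It does not remove the gap, because those safeguards rest on judgment while 10.6.1 makes the stop mandatory.

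A reader might infer that AESI status and reporting time are in irreconcilable conflict, with a mild reaction being both a 24-hour AESI and a routine event. The documents do not support that. Section 10.4.1.3 says that the study's AESIs *include* its list, which is not exclusive wording. The routine row of Table 4 covers only events that are neither serious nor AESIs ("Adverse Event (non-SAE, non-AES"). The general sentence in 10.6.1 can therefore be read as adding to the list, with the 24-hour limit following from 10.4.5. What remains is uneven wording that invites uneven flagging.

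A reader might also be tempted to count how many kinds of reaction the rules treat differently. Such a count depends on how reactions are classified and measures no risk, so none is given.

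**Conclusion.** The point holds as an inconsistency in an operative safety rule: the mandatory stop list does not carry the stops that 10.6.1 requires. It should be corrected, but its effect is small. The documents give no rate of allergic reactions, so no number of affected patients can be stated.

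The safety analysis is largely protected. SAP Table 1 finds hypersensitivity events by a standard MedDRA query, combined with corrective treatment, drug withdrawal or drug interruption, and then a blinded medical review. A reaction that is paused rather than stopped can still enter that screen. The summaries that could shift are those of events leading to permanent discontinuation and of investigator-reported AESIs.

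A reader might infer that differing stop decisions threaten the efficacy result. They do not on this plan: SAP 2.4.4.1 includes data collected after treatment discontinuation, and no sample size, power or alpha figure depends on these rules.

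The conclusion assumes that anaphylaxis, when it occurs, is treated at once. Appendix H, cited for the definition of anaphylaxis, is not in the text supplied and is not needed for the comparison.

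**What to change.** In 10.3.3, insert *or* between anaphylactic and systemic, and add a second limb for any acute allergic reaction that requires immediate treatment, with a cross-reference to 10.6.1. This keeps the broader stop. Cutting 10.6.1 down to the 10.4.1.3 wording would also give consistency, but it would drop a mandatory stop for a risk that the protocol itself highlights, so it is not recommended.

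Separately, settle which allergic reactions are AESIs and use that wording in 10.6.1, 10.4.1.3 and Table 4, so that sites flag the same events within 24 hours. How wide to set it is a clinical choice for the sponsor. The sampling rule in 9.5.1.1 should then be checked against the choice.

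The text change is one item in 10.3.3 and one harmonised AESI wording. It needs no new data collection and no SAP change. The real cost is procedural: Section 15 requires ethics approval of an amendment before it is implemented, unless there are overriding safety reasons, and about 130 sites are planned. It could travel with the next amendment.
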